IPTp	Intermittent preventive therapy in pregnancy
IRB	Institutional review board
ITN	Insecticide treated net
MOH	Ministry of Health
MU	Makerere University
NICHD	National Institute of Child Health and Human Development
NIH	National Institute of Health
SAE	Serious adverse event
SAP	Statistical Analysis Plan
SP	Sulfadoxine–pyrimethamine
TDH	Tororo District Hospital
UCSF	University California San Francisco
WHO	WHO World Health Organization

2 Introduction

2.1 Preface

In sub-Saharan Africa approximately 25 million pregnant women are at risk of *P. falciparum* infection every year and 25% have evidence of placental infection.¹ Among pregnant women living in areas of stable transmission few infections lead to symptomatic malaria, however, infection is associated with maternal morbidity, such as anemia, and adverse birth outcomes including abortions, stillbirth, preterm delivery, low birth weight (LBW), and infant mortality.^{2,3}

In Africa the only widely available tools for the prevention of malaria in pregnancy are insecticide treated bednets (ITNs) and intermittent preventive therapy (IPTp) with sulfadoxine-pyrimethamine (SP). Older studies demonstrated the efficacy of IPTp with SP in reducing the risk of placental malaria and LBW.⁴⁻⁸ However, there are now concerns about the continued efficacy of IPTp given the spread of antifolate resistance. A 2007 review suggested that IPTp with SP remained beneficial in areas with antifolate resistance, however, this conclusion was based on communities where SP treatment failure rates in children remained at moderate levels.⁹ More recently, reports from East Africa have documented SP failure rates over 65% in children when used for treatment¹⁰ or prevention¹¹, and near saturation of common SP resistance alleles.^{12,13} In a recent study from Tanzania IPTp with SP was not associated with a decreased risk of placental malaria, maternal anemia, or LBW, and unexpectedly associated with an increased risk of fetal anemia.¹⁴ In a recent study from Uganda there was no significant difference in the risk of maternal infection, maternal anemia, and LBW for pregnant women receiving IPTp with SP plus ITNs vs. ITNs alone.¹⁵ In addition, most IPTp studies have defined placental malaria on the basis of placental blood smears, which dramatically underestimate the true prevalence of placental malaria. In summary, there are several lines of evidence suggesting that IPTp with SP is no longer effective in areas of East Africa with widespread antifolate resistance. New interventions to reduce the burden of malaria in pregnancy in this region are desperately needed.

The artemisinin-based combination therapy (ACT) class of drugs offers an attractive alternative to SP for use in pregnancy. In a recent systematic review of parasitological efficacy for the treatment and prevention of falciparum malaria in pregnancy, placenta-positive rates were unacceptably high in a majority of SP trial arms and ACTs provided the lowest parasitological failure rates.¹⁶ The authors

recommended that SP should no longer be used for treatment or prevention of malaria in pregnancy and that ACTs provide the most efficacious and safe alternative therapy. Two studies of the ACT artesunate (AS) + SP from Africa concluded that this drug was safe for the treatment of malaria in pregnant women.^{17,18} More recent studies have focused on artemether–lumefantrine (AL), considering efficacy, pharmacokinetics, and safety. In a prospective study from Zambia, 495 pregnant women exposed to AL (including 156 in the 1st trimester) had similar risks of adverse maternal and infant outcomes compared to pregnant women exposed to SP.¹⁹ In a recent study from Uganda, pregnant women in their 2nd or 3rd trimester with peripheral parasitemia treated with AL had a cure rate of 99%.²⁰ Dihydroartemisinin–piperaquine (DP) has also been safely used for the treatment of uncomplicated malaria in pregnancy in studies from Asia.^{21,22} In two recent studies on the treatment of uncomplicated malaria with DP in pregnant and non-pregnant women, one concluded that there were no clinically important differences in piperazine pharmacokinetics in pregnancy²³ and another concluded that pregnancy was associated with an unaltered total exposure to piperazine but a shorter terminal elimination half-life.²⁴

In summary, most African countries continue to recommend IPTp with SP, however, there are serious concerns about the efficacy of SP given widespread resistance, especially in East Africa. Available data have shown that ACTs are effective and safe for the treatment of malaria in pregnancy and are now recommended by the WHO as 1st line therapy for pregnant women in their 2nd or 3rd trimester.²⁵ However, there are no published studies evaluating the safety and efficacy of ACTs for use as preventive therapy in pregnant women.

2.2 Purpose of the analyses

This proposal will be the first clinical trial we are aware of to evaluate the efficacy and safety of DP for the prevention of malaria in pregnant women. We will perform a randomized, double-blinded, controlled trial to compare 2 dosing strategies of this novel intervention with the current standard of care of IPTp with SP in an area of high transmission intensity and widespread antifolate resistance. The primary outcome will be based on placental histopathology; in addition, pregnant women will undergo monthly blood sampling using a highly sensitive loop-mediated isothermal amplification (LAMP) assay to better define the timing and frequency of malaria infection during pregnancy.

3 Study Objectives and Endpoints

3.1 Study Objectives

(ICH E3; 8.)

We will test the hypothesis that IPT with DP will significantly reduce the burden of malaria in pregnancy. The specific study objectives are as follows:

3.1.1. Objective 1

To compare the risk of placental malaria among HIV uninfected pregnant women randomized to receive IPTp with 3 dose SP vs. 3 dose DP vs. monthly DP. We will test the hypothesis that pregnant women who receive IPTp with either 3 doses of DP or monthly DP will have a lower risk of placental malaria defined by histopathology compared to those who receive 3 doses of SP. Secondary outcomes will include maternal and fetal clinical outcomes. We will also compare the two different dosing strategies of DP.

3.2 Endpoints

(ICH E9; 2.2.2)

3.2.1. Primary Outcomes

The primary outcome for pregnant women will be the prevalence of placental malaria based on placental histopathology and dichotomized into any evidence of placental infection (parasites or pigment) vs. no evidence of placental infection. We will also evaluate placental malaria defined by histopathology as a categorical variable (active–acute, active–chronic, and past infection) based on the criteria developed by Rogerson et al.²⁶

3.2.2. Secondary Outcomes

- **Prevalence of placental parasitemia:** Proportion of placental blood samples positive for parasites by microscopy or LAMP
- **Incidence of maternal malaria:** Episodes of fever and positive blood smear by microscopy

- **Prevalence of adverse birth outcomes:** Proportions of birth outcomes that include congenital malformations, preterm delivery, late spontaneous abortion, LBW (<2500g), stillbirth, or a composite of all of these
- **Incidence of adverse events:** Adverse events stratified by type, severity score and relationship to study drugs
- **Prevalence of anemia:** Proportion of routine hemoglobin measurements < 11 g/dL & < 8 g/dL
- **Prevalence of asymptomatic parasitemia:** Proportion of routine monthly samples positive for parasites by LAMP

3.3 Derived Variables

Composite adverse birth outcome will be a derived variable defined as the presence of any preterm delivery, congenital malformations, spontaneous abortion, low birth weight (<2500g), or stillbirth.

4 Study Methods

4.1 General Study Design and Plan

(ICH E3;9)

This will be a double-blinded randomized controlled phase III trial of 300 HIV uninfected pregnant women and the children born to them. The study interventions will be divided into two phases. In the first phase, HIV uninfected women enrolled at 12–20 weeks gestation will be randomized in equal proportions to one of three IPTp treatment arms: 1) 3 doses of SP, 2) 3 doses of DP, or 3) monthly DP. All three interventions arms will have either SP or DP placebo to ensure adequate blinding is achieved in the study. Follow-up for the pregnant women will end approximately 6 weeks after giving birth. In the second phase of the study, all children born to pregnant women enrolled in the study will be followed from birth until they reach 36 months of age. Children born to women randomized to receive 3 doses of SP during pregnancy will receive DP every 3 months between 2–24 months of age. Children born to women randomized to receive 3 doses of DP or monthly DP during pregnancy will receive either DP every 3 months or monthly DP between 2–24 months of age. To ensure adequate blinding, children who will receive DP every 3 months will be given DP placebo during the months they will not be taking DP. Children

will then be followed an additional year between 24–36 months of age following the interventions.

The details outlined in this statistical analyses plan will only focus on Phase I of the study involving pregnant women.

4.2 Equivalence or Non-Inferiority Studies

(ICH E3; 9.2, 9.7.1, 11.4.2.7. ICH E9; 3.3.2)

N/A – This trial is designed as a superiority trial.

4.3 Inclusion–Exclusion Criteria and General Study Population

(ICH E3;9.3. ICH E9;2.2.1)

4.3.1. Inclusion Criteria

- 1) Pregnancy confirmed by positive urine pregnancy test or intrauterine pregnancy by ultrasound
- 2) Estimated gestational age between 12–20 weeks
- 3) Confirmed to be HIV uninfected by rapid test
- 4) 16 years of age or older
- 5) Residency within 30km of the study clinic
- 6) Provision of informed consent by the pregnant woman for herself and her unborn child
- 7) Agreement to come to the study clinic for any febrile episode or other illness and avoid medications given outside the study protocol
- 8) Plan to deliver in the hospital

4.3.2. Exclusion Criteria

- 1) History of serious adverse event to SP or DP
- 2) Active medical problem requiring inpatient evaluation at the time of screening
- 3) Intention of moving more than 30km from the study clinic

- 4) Chronic medical condition requiring frequent medical attention
- 5) Prior SP preventive therapy or any other antimalarial therapy during this pregnancy
- 6) Early or active labor (documented by cervical change with uterine contractions)

4.4 Randomization and Blinding

(ICH E3; 9.4.3, 9.4.6. ICH E9; 2.3.1, 2.3.2)

Treatment Group Assignments

There will be 5 treatment arms which include both the intervention for the woman during pregnancy and her unborn child(ren) during infancy (Table 1). Non-singleton births from the same mother will be assigned to the same intervention. We will use a 2:1:1:1:1 randomization scheme targeting 100, 50, 50, 50, 50 pregnant women in treatment arms A–E respectively. This randomization scheme will result in a target of 100 women for each of the 3 different treatment arms during pregnancy. A randomization list will be computer generated by a member of the project who will not be directly involved in the conduct of the study. The randomization list will include consecutive treatment numbers with corresponding random treatment assignments. Randomized codes will correspond to the 5 treatment groups using permuted variable sized blocks of 6 and 12 (to account for treatment group A being represented twice as often as the other 4 treatment groups). Sealed copies of the original randomization list and documentation of the procedure used to generate the lists will be stored in the project administrative offices in San Francisco and Kampala. Prior to the onset of the study, a set of sequentially numbered, opaque, sealed envelopes will be prepared. Each envelope will be marked on the outside with the treatment allocation number. The inside of the envelope will contain a piece of paper with the treatment allocation number and treatment group assignment along with a piece of carbon paper.

Table 1. Treatment arms with assignment of study drugs during pregnancy and infancy

Phase of intervention	Treatment arm (target number)				
	A	B	C	D	E
During pregnancy	3 dose SP (100)	3 dose DP (100)		Monthly DP (100)	
During infancy	3 monthly DP (100)	3 monthly DP (50)	Monthly DP (50)	3 monthly DP (50)	Monthly DP (50)

4.5 Study Variables

(ICH E3; 9.5.1. ICH E9; 2.2.2)

See Data Dictionary Excel file for complete list of study variables.

Table 2. Schedule of routine assessments and procedures in pregnant women

Evaluations and Interventions	Enrollment	Weeks of gestation							Delivery	1 and 6 weeks postpartum
		16*	20	24	28	32	36	40		
Informed consent	X									
HIV testing ¹	X				X				X	
Pregnancy confirmation ²	X									
Obstetrical ultrasound ³	X									
Blood collected by phlebotomy for CBC, ALT, and immunology studies	X		X		X			X	X	
Blood collected by finger prick for dried blood spot and plasma	X	X	X	X	X	X	X	X	X	
Routine assessment in the study clinic ⁴	X	X	X	X	X	X	X	X		X
Administration of study drugs		X	X	X	X	X	X	X		
Collection of cord blood and placental tissue									X	
Labor and delivery documentation ⁵									X	

* Only if study subject enrolled prior to 16 weeks gestation; If the woman is enrolled between 18-20 weeks, then the week 20 phlebotomy will not be performed.

Explanation of maternal schedule of events

1. HIV test will be done at enrollment and documented. A repeat rapid HIV test will be done at delivery. HIV testing shall be done using standard rapid HIV-testing algorithm.
2. Pregnancy confirmation by positive urine pregnancy test, or confirmed intrauterine pregnancy by ultrasound. A pregnancy test may be skipped if an intrauterine pregnancy has been noted on ultrasound at the screening visit.
3. Ultrasound will be done to confirm intrauterine pregnancy and estimate gestational age at enrollment. See Appendix B for dating criteria.
4. Targeted physical exam will include anthropometric measurements (e.g. weight) and vital signs (i.e. temperature, pulse, and blood pressure). Measurement of height at the enrollment visit only.
5. Labor & Delivery documentation will include: Peripartum history, mode of delivery, Apgar scores (when available), weight, length, and head circumference of the child at birth, approximate gestational age, duration of labor, signs of fetal distress (presence of meconium), summary of events in first days of life (including feeding, breathing patterns, jaundice, lethargy, or any additional abnormal findings), duration of admission if delivered in hospital.

Table 3. Study Case Report Forms

CRF#	Form/Questionnaire
1	BC-1 Screening
2	BC-1 Enrollment
3	BC-1 Clinic Visit Form
4	BC-1 Subject Hospital Admission
5	BC-1 Missed Visit Form
6	BC-1 Subject Death Record Form
7	BC-1 Mothers Delivery Form
8	BC-1 Postpartum Visit Form
9	BC-1 Child's Delivery Form
10	BC-1 Study Drug Dispensing Forms
11	BC-1 AE Forms
12	BC-1 Subject Withdrawal or Study Completion Form
13	BC-1 Household Survey Questionnaire
14	BC-1 GPS Coordinates
15	BC-1 Placental Histopathology

5 Sample Size

(ICH E3; 9.7.2. ICH E9; 3.5)

The number of pregnant women enrolled and the number of study participants reaching the various endpoints will determine the samples sizes for each of the primary outcomes of our study aims (Table 4). The 3 primary hypotheses for the complete study are as follows: 1) We will test the hypothesis that pregnant women who receive IPTp with either 3 dose DP or monthly DP will have a lower risk of placental malaria defined by histopathology compared to those who receive 3 doses of SP. We will also compare the two different dosing strategies of DP. 2) We will test the hypothesis that infants randomized to receive monthly DP between 2–24 months of age will have a lower incidence of malaria during the first 24 months of life compared to infants randomized to receive q 3 monthly DP. 3) We will test the hypotheses that a) infants born to mothers randomized to receive IPTp with 3 dose DP or monthly DP will have a lower incidence of malaria during the first 24 months of life compared to infants born to mothers who were randomized to receive IPTp with 3 doses of SP, and b) infants randomized to receive monthly DP between 2–24

months of age will have a lower incidence of malaria between 24–36 months of age after the intervention is stopped compared to infants randomized q 3 monthly DP between 2–24 months of age. The primary determinant of our target sample size was based on testing hypotheses 3 given that the magnitude of differences anticipated for this hypothesis would be smaller than those anticipated for hypothesis 1 and 2. We conservatively estimate that 90% of pregnant women enrolled will reach the primary study endpoint and we will lose 5% of follow-up time per year in the infants. The minimum relative differences detectable for the primary outcomes of the 3 hypotheses given our estimated sample sizes are summarized in Table 5 below. For hypotheses 1, we will be powered to detect a 33% relative difference in the prevalence of placental malaria in the 3 dose DP arm or the monthly DP arm compared to the 3 dose SP arm assuming a prevalence of placental malaria of 62% in the 3 dose SP arm based on prior data. We will also be powered to detect a 41–70% relative difference in the prevalence of placental malaria in the monthly DP arm compared to the 3 dose DP arm assuming a prevalence of placental malaria in the 3 dose DP arm ranging from 20–50%. For hypothesis 2, we will be powered to detect an 18–23% relative difference in the incidence of malaria between 0–24 months of age in the monthly DP arm compared to the q 3 monthly DP arm assuming an incidence of malaria in the q 3 monthly DP arm ranging from 3–5 episodes PPY. For hypothesis 3A, we will be powered to detect a 22–28% relative difference in the incidence of malaria between 0–24 months of age among children assigned to receive q 3 monthly DP when comparing those born to women who received 3 dose SP to those born to women who received 3 dose DP or monthly DP assuming an incidence of malaria in the control group ranging from 3–5 episodes PPY. For hypothesis 3B, we will also be powered to detect a 16–21% relative difference in the incidence of malaria between 24–36 months of age among children assigned to receive monthly DP during infancy compared to those who received q 3 monthly DP during infancy assuming an incidence of malaria in the control group ranging from 3–5 episodes PPY.

Table 4. Intervention arms during pregnancy and infancy

Study populations	Intervention arms				
	3 doses of SP	3 doses of DP		monthly DP	
Assigned treatment arms in pregnant women	3 doses of SP	3 doses of DP		monthly DP	
Estimated number of pregnant women enrolled	100	100		100	
Estimated number with placental outcomes	90	90		90	
Assigned treatment arms in infants	q 3 monthly DP	q 3 monthly DP	monthly DP	q 3 monthly DP	monthly DP
Estimated number of infants enrolled	90	45	45	45	45
Estimated number of infants reaching 24 months of age	81	41	41	41	41

Table 5. Minimum relative differences in outcomes detectable given estimated effective sample sizes

Hypothesis	Analysis population	Control group and estimated sample size	Comparison group and estimated sample size	Estimated outcome measure in control group	Minimum relative difference detectable*
1	Pregnant women with placental malaria measured by histopathology at birth	3 dose SP (n=90)	3 dose DP or monthly DP (n=90 each)	Prevalence of placental malaria = 62%	33%
		3 dose DP (n=90)	monthly DP (n=90)	Prevalence of placental malaria = 20-50%	41-70%
2	Infants 0-24 months of age born to women assigned to receive IPTp with 3 dose DP or monthly DP	Infants assigned q 3 monthly DP (n=90)	Infants assigned monthly DP (n=90)	Incidence of malaria = 3-5 episode PPY	18-23%
3	Infants 0-24 months of age randomized to q 3 monthly DP	Infants of women assigned 3 dose SP (n=90)	Infants of women assigned 3 dose DP or monthly DP (n=45 each)	Incidence of malaria = 3-5 episodes PPY	22-28%
	Infants 24-36 months of age after chemoprevention stopped	Infants assigned q 3 monthly DP (n=163)	Infants assigned monthly DP (n=82)	Incidence of malaria = 3-5 episodes PPY	16-21%

* Relative difference = (estimated outcome in control arm – estimated outcome in the comparison arm) / estimated outcome on the control arm (two-sided alpha = 0.05, power = 80%).

6 General Considerations

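### Table 5's detectable differences for infant hypotheses 2 and 3A match one person-year per infant, although both outcomes cover 0–24 months (about 1.9 person-years)

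*SAP*

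**What the plan says.** Section 5 and Table 5 of the SAP give minimum detectable relative differences for three infant comparisons. All assume a control rate of 3–5 episodes per person-year, and the Table 5 footnote sets "two-sided alpha = 0.05, power = 80"%.

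- **Hypothesis 2** (90 vs 90 infants): "we will be powered to detect an 18–23% relative difference in the incidence of malaria between 0–24 months of age".
- **Hypothesis 3A** (90 vs 45 infants): "we will be powered to detect a 22–28% relative difference in the incidence of malaria between 0–24 months of age". Table 5 labels this population "Infants 0-24 months of age randomized to q 3 monthly DP".
- **Hypothesis 3B** (163 vs 82 infants): 16–21%, over 24–36 months of age.

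On follow-up, Section 5 assumes that "we will lose 5% of follow-up time per year in the infants". The Table 4 row "Estimated number of infants reaching 24 months of age" shows 81 of 90 in the SP group and 41 of 45 in each of the other four groups. On the role of these figures, Section 5 says: "The primary determinant of our target sample size was based on testing hypotheses 3".

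Section 5 states neither the person-time per infant nor a variance model behind the three ranges.

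**The concern.** The rates are per person-year, so the information in each comparison depends on person-years as well as on the number of infants. A 0–24 month window carries nearly twice the person-time of a 24–36 month window. With the same group sizes, the detectable difference should therefore shrink by a factor of about √1.9 ≈ 1.38. The printed ranges for hypotheses 2 and 3A show no sign of this.

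Hypothesis 3A is one of the two parts of the hypothesis said to have set the sample size, and its entry does not follow from the window, rates and follow-up loss stated beside it. A reader cannot tell whether the second year was overlooked or a margin was built in without being named. The two explanations have opposite consequences. If the year was overlooked, hypotheses 2 and 3A are better powered than stated. If a margin was intended, 3B lacks it and its 16–21% is too favourable.

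**Working it through.** **Inputs (Section 5, Tables 4 and 5).** Two-sided alpha 0.05 (z = 1.960), power 80% (z = 0.842), control rate r = 3 or 5 per person-year. The relative difference d is (control − comparison)/control, as the Table 5 footnote defines it.

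**Formula.** Two-sample Poisson rates with person-years P₁ (control) and P₂ (comparison):

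r·d = 1.960·√[r̄(1/P₁ + 1/P₂)] + 0.842·√[r/P₁ + r(1−d)/P₂]

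where r̄ = [P₁r + P₂r(1−d)]/(P₁+P₂). This is solved for d. A log rate ratio version was run as a cross-check.

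**Step 1: reproduce the printed figures.** Set one person-year per infant. For hypothesis 2 at r = 3, P₁ = P₂ = 90, try d = 0.227. The comparison rate is 2.319 and r̄ = 2.6595. The right side is 1.960·√(2.6595·2/90) + 0.842·√(5.319/90) = 0.476 + 0.205 = 0.681, which equals 3 × 0.227.

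| Row | Printed | Pooled, r = 5 to 3 | Log rate ratio, r = 5 to 3 |
|---|---|---|---|
| 2 (90 vs 90) | 18–23% | 17.8–22.7% | 17.9–22.8% |
| 3A (90 vs 45) | 22–28% | 21.8–27.7% | 22.1–28.2% |
| 3B (163 vs 82) | 16–21% | 16.3–20.9% | 16.5–21.2% |

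In the pooled form, all six printed endpoints are recovered on rounding. For 3B, one person-year is the length of the window.

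**Step 2: person-years over 0–24 months.** From Table 4, with even loss:

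- 90 infants falling to 81: (90 + 81)/2 × 2 years = 171, or 1.9 per infant.
- 45 infants falling to 41: (45 + 41)/2 × 2 years = 86, or about 1.9 per infant.
- Each hypothesis 2 arm is two groups of 45: 2 × 86 = 172.

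**Step 3: recompute.** For hypothesis 2 at r = 3, P = 172 per arm, d = 0.167: the comparison rate is 2.499 and r̄ = 2.7495. The right side is 0.350 + 0.150 ≈ 0.501 = 3 × 0.167.

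| Row | Table 4 person-years | 2.0 per infant, no loss |
|---|---|---|
| 2 | 13.1–16.7% | 12.8–16.3% |
| 3A, pooled | 16.0–20.4% | 15.6–20.0% |
| 3A, log rate ratio | 16.1–20.7% | 15.8–20.2% |

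**Step 4: power at the printed differences, Table 4 person-years.** Hypothesis 2: about 97.5% at both ends. Hypothesis 3A: 97.6–97.7% pooled, 97.0–97.1% log rate ratio. At 1.9–2.0 person-years per infant, the printed differences would need about 44–47 infants per arm for hypothesis 2 (Table 5 has 90). For 3A they would need about 44–48 vs 22–24 (Table 5 has 90 vs 45).

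**Step 5: other explanations.**

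- *Completers only.* With 82 vs 82 and 81 vs 41 infants at 1.9 person-years each, the pooled results are 13.7–17.5% and 16.8–21.4%, still well below the printed ranges.
- *Constant variance inflation.* A factor of about 1.9 recovers hypotheses 2 and 3A. The same factor puts 3B at about 22–28% pooled (23–29% log rate ratio), against the printed 16–21%.
- *Negative binomial.* Hypothesis 2 needs a dispersion of about 0.11 at 5 per person-year but 0.19 at 3. At dispersion 0.10, 3B would already be about 20–24%.

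**The case against.** The strongest reply is that little turns on this. The SAP limits itself to Phase I, the pregnant women, and hypotheses 2 and 3A are infant hypotheses that none of its analyses serve. The discrepancy errs on the safe side: a comparison said to have 80% power has more. Section 5 names hypothesis 3 as a whole as the driver of sample size, and the 3B part is sound. The one-year basis is also inferred from a numerical match, since the SAP does not state it. All of this stands, and it limits the weight of the point. It does not make the printed figures follow from the inputs beside them.

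A second reply concerns the replacement figures. For other incidence outcomes, Sections 8.3 and 9.3 foresee overdispersion and negative binomial models, so plain Poisson figures may be optimistic. With an assumed dispersion of 0.10–0.20 at 1.9 person-years, hypothesis 2 would be about 18–20% to 21–23%, and 3A about 22–25% to 25–28%, close to what is printed. That is a fair caution, and a reason to state the variance model. It does not rescue the table, because no single dispersion gives both ends of the hypothesis 2 range and any of these values raises 3B above its printed range.

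A smaller point: applying the yearly loss within the third year too (about 0.975 person-years) moves 3B to about 16.5–21.1% pooled, or 16.7–21.4% on the log rate ratio. The effect is negligible.

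**Conclusion.** The concern holds. On the inputs in Section 5 and Table 4, with Poisson variance and 1.9–2.0 person-years per infant, the detectable differences are about 13–17% for hypothesis 2 (printed 18–23%) and about 16–21% for 3A (printed 22–28%). Power at the printed values is about 97–98%, not 80%. Hypothesis 3B is consistent with its own window.

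That the second year was left out is the explanation that fits all three rows, but it is an inference. The conclusion that the rows do not share one stated basis needs no such inference. The error is conservative under Poisson variance and changes neither enrolment nor any Phase I analysis, hypothesis 1 included. It should be corrected because it is a wrong power statement on a hypothesis the SAP says set its sample size.

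**What to change.** In the Table 5 footnote, state the person-years per infant used in each infant row and the variance model. Then take one of two routes:

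- **Plain Poisson.** Restate hypothesis 2 as about 13–17% and 3A as about 16–21%, in Table 5 and in the matching sentences of Section 5. Leave 3B at 16–21%.
- **Overdispersion allowance.** If the larger values were meant to include one, name the factor and apply it to every infant row. As an illustration only, an assumed variance of twice the mean would put 3B at about 23–30% (22.8–28.9% pooled, 23.1–29.5% log rate ratio).

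The first route costs two table entries, two sentences and a footnote. The second also makes the 3B figure less favourable. Neither changes planned enrolment or the Phase I analyses.

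### Table 5's hypothesis 3B row (163 vs 82) counts all 81 infants of SP mothers as controls, confounding infant regimen with maternal arm; without them 16–21% becomes about 19–24%

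*SAP*

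**What the plan says.** Section 5 of the SAP sizes the whole study, including the infant phase. It states that "The primary determinant of our target sample size was based on testing hypotheses 3". For 3B, the infant-regimen comparison after chemoprevention stops, it says "we will also be powered to detect a 16–21% relative difference in the incidence of malaria between 24–36 months of age", with control incidence of 3–5 episodes per person-year (PPY), two-sided alpha 0.05 and 80% power.

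The 3B row of Table 5 sets "Infants assigned q 3 monthly DP (n=163") against "Infants assigned monthly DP (n=82") and does not restrict by maternal arm. The source of these counts is the last row of Table 4, "Estimated number of infants reaching 24 months of age": 81, 41, 41, 41 and 41 for arms A to E. Section 4.1 and Table 1 assign every child of an SP mother (arm A) to DP every 3 months. Only the two maternal DP arms are split between the two infant regimens.

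Hypothesis 2 makes the same infant-regimen contrast over 0–24 months. Its wording, "infants randomized to receive monthly DP between 2–24 months of age will have a lower incidence of malaria during the first 24 months", carries no maternal restriction either, yet its Table 5 row is limited to "Infants 0-24 months of age born to women assigned to receive IPTp with 3 dose DP or monthly DP", at 90 vs 90.

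**The concern.** Arm A contributes infants to one side of the 3B contrast only. All five arms are randomised, but once arms A, B and D are pooled against C and E, the groups differ in maternal IPTp as well as infant regimen. Hypothesis 3A itself posits that maternal arm changes infant malaria incidence through 24 months. The SAP does not say that any such effect has gone by 24–36 months, and the 163 vs 82 row needs that to isolate the infant regimen.

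Two things are at stake:

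- If the infant analysis restricts to DP mothers or adjusts for maternal arm, 16–21% is too favourable. The SP stratum contains no infants on monthly DP, so adjustment cannot recover any information on infant regimen from it.
- If the analysis pools without adjustment, part of any lasting maternal effect is read as an effect of the infant regimen.

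This is one of the two printed figures for the hypothesis that Section 5 names as driving the sample size.

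**Working it through.** **Inputs.** Table 4: 81/41/41/41/41 infants at 24 months. Table 5: 3–5 episodes PPY, two-sided alpha 0.05, power 80%. Section 4.1: one further year of follow-up, 24–36 months. Section 5: "we will lose 5% of follow-up time per year in the infants".

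**Counts**
- Control: 81 + 41 + 41 = 163 (arms A, B, D).
- Comparison: 41 + 41 = 82 (arms C, E).
- Share of controls with SP mothers: 81/163 = 49.7%. Share of comparison infants: 0/82.

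**Method (assumed, because the SAP names none).** Two-sample comparison of Poisson rates with pooled variance under the null. With control rate λ, relative difference r, comparison rate λ(1−r), pooled rate λ̄ = [n₁λ + n₂λ(1−r)]/(n₁+n₂) and t person-years per infant, solve

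λr = 1.96·√[λ̄(1/n₁+1/n₂)/t] + 0.842·√[(λ/n₁ + λ(1−r)/n₂)/t].

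**Reproducing the printed infant rows (t = 1)**

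| Row | n | 5 PPY | 3 PPY | Printed |
|---|---|---|---|---|
| Hypothesis 2 | 90 vs 90 | 17.8% | 22.7% | 18–23% |
| 3A | 90 vs 45 | 21.8% | 27.7% | 22–28% |
| 3B | 163 vs 82 | 16.3% | 20.9% | 16–21% |

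Worked example, 3B at 5 PPY: r = 0.1635 gives a comparison rate of 4.183 and λ̄ = 4.726. The standard errors are 0.2943 (null) and 0.2858 (alternative), and 1.96 × 0.2943 + 0.842 × 0.2858 = 0.817 = 5 × 0.1635. The method matches all three rows.

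**3B without arm A**

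| n | t | 5 PPY | 3 PPY |
|---|---|---|---|
| 163 vs 82 | 1.00 | 16.3% | 20.9% |
| 163 vs 82 | 0.95 | 16.8% | 21.4% |
| 82 vs 82 | 1.00 | 18.6% | 23.7% |
| 82 vs 82 | 0.95 | 19.1% | 24.3% |

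Here t = 1.00 is the full 12-month window, and t = 0.95 takes the stated 5% yearly loss as lost person-time. On either basis 82 vs 82 rounds to 19–24%. Unpooled Wald and log rate ratio versions at t = 1 give 18.6–23.7% and 18.7–23.8%.

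**Power at the printed differences**

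| n | t | 16% at 5 PPY | 21% at 3 PPY |
|---|---|---|---|
| 163 vs 82 | 1.00 | 78.2% | 80.5% |
| 163 vs 82 | 0.95 | 76.0% | 78.4% |
| 82 vs 82 | 1.00 | 66.6% | 69.2% |
| 82 vs 82 | 0.95 | 64.4% | 67.0% |

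**Share of information from arm A.** Effective size 1/(1/n₁ + 1/n₂) is 54.6 for 163 vs 82 and 41.0 for 82 vs 82. The ratio is 0.752, so about 25% of the information comes from arm A.

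**Illustration of bias.** The SAP gives no maternal effect at 24–36 months, so take a residual maternal reduction d as an assumption, with no infant-regimen effect. The apparent rate ratio is (1−d) ÷ {[81 + 82(1−d)]/163}:
- d = 5%: 0.975, an apparent reduction of about 2.5%.
- d = 10%: 0.948, about 5.2%.
- d = 20%: 0.889, about 11%.

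**The case against.** The strongest reply is that nothing is miscalculated. Hypothesis 3B is worded without a maternal restriction, 163 vs 82 is exactly that population, and 16–21% is correct for it; 19–24% belongs to a narrower population. The maternal effect in 3A is posited only for 0–24 months, so the plan may have restricted hypothesis 2, which covers that period, and deliberately pooled 3B, which comes after it. Without a residual maternal effect, pooling is valid and more efficient. This SAP covers only the Phase I analyses, so the 3B model may be fixed elsewhere. Finally, 3A at 22–28% stays less favourable than 3B at 19–24%, so the change does not show that the study is too small.

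Much of this stands. The arithmetic is right, the size of any bias is unknown, the absence of a 3B model here is no defect, and no change to the target of 300 women follows. Part of the power shortfall is rounding, since 163 vs 82 itself reaches only 76–78% at the printed 16%; removing arm A costs about 11–12 points.

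The reading that the maternal effect ends at 24 months does not rescue the row, because the SAP states it nowhere. Hypothesis 2 is also worded without restriction and was still restricted in Table 5. The 3A row likewise holds infant regimen fixed. Only 3B leaves the other factor unbalanced, and no reason is given.

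**Conclusion.** The point holds and should be fixed. The 3B row pools infants in a way that confounds infant regimen with maternal arm, and its 16–21% depends on an unstated assumption of no maternal effect at 24–36 months. The comparison free of that assumption is 82 vs 82, with a detectable difference of about 19–24%, some 3 percentage points larger. The 19–24% rests on Poisson counts without overdispersion, which the printed infant figures also appear to assume, and on 0.95–1.0 person-year per infant; overdispersion would widen both ranges. The finding concerns the sample-size statement in Section 5, not the analysis of the pregnant women.

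**What to change.** In the second hypothesis 3 row of Table 5, limit the 24–36 month population to infants of women in the two DP arms, as the hypothesis 2 row does. Show 3-monthly DP (n=82) against monthly DP (n=82) at 3–5 episodes PPY, with a minimum detectable difference of 19–24%. In the 3B sentence of Section 5, replace 16–21% with 19–24% and add that the children are those born to women in the 3 dose DP or monthly DP arms.

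If the infant-phase plan pools arm A on purpose, Section 5 should at least state the assumption of no maternal-arm effect at 24–36 months and print 19–24% beside 16–21%.

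The cost is one row and one sentence. It needs no new participants and no change to the Phase I analysis. The price is a stated detectable difference about 3 percentage points less favourable.
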